PROJECT VISION (PI: [name]; Livestrong; 2003-05) enrolled 62 (86% participation rate) adult-aged Hodgkin lymphoma survivors at increased risk for either breast cancer or cardiomyopathy to test the acceptability of an IOM-based SCP supplemented by a study website and an effort to engage participants' primary care providers.⁴³ 92% of participants completed a 6-month post-intervention survey; 75% remembered receiving, reading, and understanding the SCP. Among participants, prior knowledge of mammogram and echocardiogram screening recommendations was low (32% and 12% respectively). During the 6-month study period, 41% and 20% of eligible respondents obtained a mammogram and echocardiogram, respectively, with another 35% (for both tests) planning to do so

FIGURE 3. Yield of directly measured data in relation to self-report among randomly selected CCSS participants (n=175).

*Per self-report. †Among those with self-reported condition if home sampled value was beyond standard therapeutic range. ‡No prior self-reported history of respective condition with abnormal value.

within the next 6 months. As such, these data guide our planned intervention follow-up period of 12 months between assessments. Similar to other studies,⁴⁴ website usage was limited among these young adult survivors (29% visit rate). Primary care providers demonstrated limited engagement: only 19% of providers volunteered to participate; none visited the study website or contacted the study team.⁴³

The ECHOS trial (co-PI: [name]; R01 CA136912; 2009-13) extended the methods in VISION to directly test the efficacy of a SCP supplemented by 2 nurse practitioner-led phone self-management counseling sessions on cardiomyopathy screening (vs. mailed SCP alone).⁴⁵ After 1-year, the randomized intervention group had higher rates of obtaining recommended echocardiograms per self-report validated by medical records (52% vs. 22% SCP alone [$p<0.001$]; RR 2.3, 95% CI 1.7-3.1). The intervention group also was less likely to report lack of physician recommendation as a reason for not obtaining an echocardiogram, suggesting that the counseling further enhanced communication between recipients and their primary care provider beyond what a SCP alone would have accomplished.⁴⁶ The study had an 87% retention rate at 1-year follow-up (n=411 of 472).⁴⁵

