- **Diabetes:** American Diabetes Association classifies fasting blood glucose 100-125 mg/dL or HbA1c 5.7-6.4% as suggestive of impaired glucose tolerance (pre-diabetes). Similar to dyslipidemia, as fasting blood draws are not as commonly done in most primary care settings now for initial screening, for non-fasting (<8 hours) samples, blood glucose 140-199 mg/dL will be classified as suggestive of pre-diabetes if HbA1c was <5.7%. *Lifestyle intervention* is recommended (metformin prevention considered for select high risk populations).⁵⁴ Diabetes requires fasting blood glucose ≥ 126 mg/dL or HbA1c $\geq 6.5\%$. If not-fasting, random blood glucose ≥ 200 mg/dL would be concerning for diabetes if HbA1c was $<6.5\%$. In addition to lifestyle modifications, *metformin* is typically started with additional agents as indicated. We will ascertain the prevalence of pre-diabetes and diabetes; both may be eligible for Aim 2.

Undertreatment defined for each as:

- While any participant who was previously undiagnosed is also technically undertreated, we will reserve this definition to those who previously or currently reported to CCSS as being diagnosed with hypertension, dyslipidemia, or diabetes (either managed by lifestyle modifications or medication therapy), if their home-sampled value falls outside the recommended therapeutic range: blood pressure $\geq 130/80$ mmHg, LDL ≥ 160 mg/dL, triglyceride ≥ 150 mg/dL (if fasting <10 hours: ≥ 200 mg/dL), or HbA1c $\geq 7.0\%$ (different than the HbA1c diabetes diagnosis threshold⁶⁵).

3.3.2 **Primary Aim 2 Endpoint:** Probability of intervention subjects having an undertreated CV condition compared with the control group at 1-year follow-up.

3.3.3 **Primary Aim 3 Endpoint:** Barriers among survivors and their primary healthcare providers that contribute to undertreatment of hypertension, dyslipidemia, and diabetes.

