6.0 SUBJECT RECRUITMENT & REGISTRATION

6.1 Recruitment

A list of eligible patients for Aim 1 will be generated using existing CCSS data. Staff at the CCSS Data Coordinating Center at St. Jude will be responsible for sending out approach packets to these patients (introductory letter, Consent, Healthcare Provider Form, HIPAA, study questionnaire, and upfront honorarium). We will also have the Consent/ Healthcare Provider Form/ HIPAA Form and the study questionnaire available online. For non-responders, St. Jude interviewers will follow-up with phone calls using their standard process. *As part of St. Jude's standard CCSS process for other CCSS activities, participants will have the option of indicating consent by signing the paper form, signing an online consent, or by providing verbal consent to a CCSS St. Jude interviewer.* Similarly, questionnaires can also be completed by interview.

With our 12/2017 protocol modification, we will also pilot alternative approach packets to see if smaller packets that request less of participants upfront can improve accrual. Specifically, in addition to the existing approach process, we will pilot a 2nd process by which we exclude the printed study questionnaire from the approach packet (an option to complete this on-line will still be mentioned in the cover letter). Participants who consent in this fashion but who do not complete the on-line questionnaire will then be sent a paper version. A 3rd process will also be piloted which will feature a tiered consent process by which the initial consent will just be to complete the initial home visit without consenting to the subsequent randomized intervention trial. For those participants who consent in this fashion, after they complete the initial home visit and are found to be eligible for the randomized intervention trial, they will then receive the second consent form that describes the trial. If one of these alternative approach processes results in a substantially higher enrollment rate, that process will then be adopted as our standard approach.

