13.0 STATISTICAL CONSIDERATIONS

13.1 Aim 1 Analytic Plan

Hypothesis: Approximately 60% of participants will have an abnormal CV risk-factor finding that meets clinical intervention thresholds, and among those with abnormalities, 40% will be undertreated and 80% newly diagnosed.

Primary analyses: We will calculate the prevalence of hypertension, dyslipidemia, and diabetes by self-report and by physiologic measurement. We will then calculate the proportions (with exact 95% confidence intervals) of participants who may be underdiagnosed as well as the proportions undertreated (like **Figure 3**). We will calculate the prevalence of directly measured pre-diabetes separately. **Secondary analyses:** We will examine whether rates differ by: sex; current age; time since cancer diagnosis; obese ($BMI \geq 30 \text{ kg/m}^2$) vs. not; health insurance vs. not; recent history of being seen in a dedicated long-term follow-up clinic for survivors vs. not; and lifestyle factors (smoking, low fruit/vegetable intake, low physical activity).

Sample size considerations: Based on prevalence estimates from CCSS surveys and our pilot (**Table 2, Figure 3**), we expect ~60% of high CV risk participants ($n \sim 480$) to have an abnormal CV risk factor measurement; prevalence of individual risk factors ranging 20-40% (less when stratified by underdiagnosis/undertreatment status). With an overall sample $n=800$, we expect reasonable precision for our primary prevalence estimates (**Table 9**). Power to detect differences <10% in secondary analyses may be more limited.

TABLE 9. Estimated power for Aim 1 analyses.		
Prevalence \pm 95% CI	Minimum detectable proportions*	
N=800	N=320:480	N=200:200
5% \pm 1.5%	5% vs. 1/11%	5% vs. 0/14%
20% \pm 2.8%	20% vs. 12/29%	20% vs. 10/33%
50% \pm 3.5%	50% vs. 40/60%	50% vs. 36/64%

*2-sample Fisher's exact test, 80% power, $\alpha=0.05$.

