Potential pitfalls / solutions: Our EMSI pilot achieved 60% enrollment. Funding from this proposal will enhance recruitment rates by providing an upfront (rather than conditional) participation incentive, which has been associated with higher rates of study participation.^{62,63} We will closely examine the demographic characteristics, past cancer treatment exposures, and self-reported burden of CV and other chronic conditions of survivors who are approached vs. not approached, and who ultimately participate vs. not. If differences are found, we will apply inverse probability weighting as a way to assess the sensitivity of our estimates.

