Potential pitfalls / solutions: We will closely monitor rates of abnormalities identified in Aim 1, as that influences the number of survivors eligible for Aim 2. As discussed earlier, we will oversample survivors known to have rarer target conditions (e.g., diabetes) such that the power to detect differences in Aim 2 is enhanced. Separately, given the nature of the intervention, participants and the study clinician cannot be blinded. However, exam staff will be blinded to randomization status.

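### Oversampling survivors with known diabetes biases the unweighted primary Aim 1 prevalence figures for that condition

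*Combined protocol and SAP*

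**What the plan says.** The commitment is in section 13.2, under potential pitfalls: "we will oversample survivors known to have rarer target conditions (e.g., diabetes) such that the power to detect differences in Aim 2 is enhanced". The sentence refers back to an earlier discussion, but the readable text of the design, accrual, eligibility and recruitment sections contains none. Section 6.1 says only: "A list of eligible patients for Aim 1 will be generated using existing CCSS data".

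Section 13.1 defines the primary Aim 1 analysis as the prevalence of each condition by self-report and by measurement, followed by "the proportions (with exact 95% confidence intervals) of participants who may be underdiagnosed as well as the proportions undertreated (like Figure 3". It mentions no weights or strata. The target population in section 3.1.1 is CCSS participants predicted to be at high cardiovascular risk.

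Section 3.3.1 makes prior diagnosis part of the undertreatment endpoint: "we will reserve this definition to those who previously or currently reported to CCSS as being diagnosed with hypertension, dyslipidemia, or diabetes".

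Section 13.1 has one safeguard. The investigators will compare, among other things, the "self-reported burden of CV and other chronic conditions of survivors who are approached vs. not approached", and participants with non-participants. It continues: "If differences are found, we will apply inverse probability weighting as a way to assess the sensitivity of our estimates".

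**The concern.** The variable used to oversample, a diagnosis already known to CCSS, is itself one Aim 1 estimand (self-reported prevalence) and a precondition for another (undertreatment). Raising the share of known cases raises both in an unweighted whole-sample proportion. It lowers whole-sample underdiagnosis of the same condition, because undiagnosed cases all lie in the group that is not oversampled. Aim 1 is a named primary aim. Without weights, its headline figure for the oversampled condition would partly describe the recruitment mix instead of high-risk CCSS survivors.

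The denominator matters too, and the plan is not explicit about it. Table 9 sets precision at N=800. The section 13.1 hypothesis is framed as "among those with abnormalities, 40% will be undertreated and 80% newly diagnosed". The Figure 3 note in section 2.2 reads "Among those with self-reported condition if home sampled value was beyond standard therapeutic range". Only a whole-sample denominator carries the undertreatment bias; the proportion undertreated among people already diagnosed does not.

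**Working it through.** **The plan's own precision figures.** Half-width = 1.96·√(p(1−p)/800) gives 1.51, 2.77 and 3.46 points at p = 5%, 20% and 50%. Table 9 states 1.5, 2.8 and 3.5. Table 9 therefore assumes simple random sampling of 800, with no allowance for unequal selection.

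**Inputs.** n = 800 comes from section 13.1. The following are assumptions, because the readable text does not give them:
- share of the target population with known diabetes, π = 5–10%
- share of those who are undertreated, u = 40–50%
- oversampling factor, k = 1.25–3

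**Formulas.** The share of known cases in the sample is s = kπ/(kπ + 1 − π). The bias in self-reported prevalence is s − π. The bias in whole-sample undertreatment is (s − π)·u.

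Example: π = 5%, k = 2 gives s = 0.10/(0.10 + 0.95) = 9.52%. With u = 40%, undertreatment moves from 2.0% to 3.81%, a bias of 1.81 points.

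| k | Self-reported prevalence: bias at π = 5% / 10% (points) | Undertreated, true 2.0% (π = 5%, u = 40%): sample shows | Undertreated, true 5.0% (π = 10%, u = 50%): sample shows |
|---|---|---|---|
| 1.25 | 1.17 / 2.20 | 2.47% | 6.10% |
| 1.5 | 2.32 / 4.29 | 2.93% | 7.14% |
| 2 | 4.52 / 8.18 | 3.81% | 9.09% |
| 3 | 8.64 / 15.00 | 5.45% | 12.5% |

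**Against sampling error.** The half-width is 0.97 points at 2% and 1.51 at 5%. The undertreatment bias equals the half-width at k = 1.52 (π = 5%, u = 40%), 1.38 (8%, 50%) and 1.35 (10%, 50%). For self-reported prevalence at π = 5%, it reaches the 1.5-point half-width at k = 1.32.

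**Coverage.** Exact (Clopper–Pearson) 95% intervals, evaluated over the binomial distribution with n = 800, cover the true undertreatment prevalence 86% to 71% of the time at k = 1.25 and 60% to 27% at k = 1.5. For self-reported prevalence, coverage is 68% to 50% at k = 1.25 and 21% to 4% at k = 1.5. In each pair the first figure is for π = 5% and the second for π = 10%.

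**Underdiagnosis.** If the true whole-sample value is 20% (assumed), the sample shows (1 − s)·0.20/(1 − π). That is 19.5–19.8% at k = 1.25 and 16.7–18.2% at k = 3, against a half-width of 2.8 points.

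**Precision after weighting.** Weights are 1/k for known cases and 1 otherwise; the design effect is the linearized variance of the weighted mean divided by the simple-random-sample variance. At π = 8% and k = 2 to 3:

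| Endpoint | Design effect | Half-width (points) |
|---|---|---|
| Undertreated diabetes (u = 50%) | 0.56 to 0.42 | 1.36 becomes 1.02 to 0.88 |
| Underdiagnosis at 20% | 1.07 to 1.15 | 2.77 becomes 2.87 to 2.97 |
| Endpoints unrelated to the stratum | 1.04 to 1.10 | – |

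**The case against.** The strongest reply is that the section 13.1 weighting already handles this. It compares approached with not-approached survivors on self-reported cardiovascular burden, which captures the oversampling variable, and oversampling of any material size would show up there. That is right as far as detection goes. But these selection probabilities are set by the investigators, so weighting should not wait for a difference to be found, and the plan keeps the unweighted figure as primary.

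A second reply is that undertreatment may be meant among those already diagnosed, as the Figure 3 note can be read. On that reading undertreatment is unbiased by this mechanism. Figure 3 itself is not in the text available for review and may settle the point. Self-reported prevalence is a whole-sample figure on any reading, however, and it shows the larger bias.

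Third, the size is assumed, and 3-fold may not be feasible. With the pilot's 60% consent and 90% completion, 800 completers need 800/(0.60 × 0.90) ≈ 1,480 approaches. At π = 8% and k = 3, s = 20.7%, so about 307 of those approached would be known cases. That requires about 307/0.08 ≈ 3,800 eligible survivors. Table 1 lists 2,059 and 764 high-risk survivors in the original cohort, possibly overlapping; the full cohort is larger. This casts doubt on the top of the range but not on factors near the break-even.

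Fourth, the underdiagnosis shift is small: at most about 1 point at 1.5-fold. That stands. So does the narrow scope: diabetes is the only condition named, and others shift only if they are also oversampled or through comorbidity.

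Finally, a figure missing from the Recruitment section could hold the earlier discussion of oversampling. Even so, section 13.1 would still lack weights in the primary analysis.

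**Conclusion.** The concern holds. Oversampling on known diagnosis combined with an unweighted primary estimator biases Aim 1 prevalence for the oversampled condition: upward for self-reported disease and whole-sample undertreatment, downward for underdiagnosis. The direction follows from the plan's text. The size rests on the assumed base rate, undertreated share and factor.

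For undertreated diabetes the overstatement is inside sampling error at 1.25-fold, though interval coverage already suffers, and exceeds the half-width from about 1.35- to 1.52-fold. At 3-fold it would be 3.5 to 7.5 points. The planned sensitivity weighting is a real but partial safeguard. This should be fixed, but it does not threaten the trial: the randomized Aim 2 comparison is untouched, as are proportions within the diagnosed group.

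**What to change.** - State in sections 6.1 and 13.1 which conditions define the oversampling strata and the sampling fraction in each. If oversampling is not being done, delete the sentence in section 13.2.
- State the denominator for every Aim 1 proportion.
- Make the design-weighted whole-sample prevalence, with design-based 95% intervals, the primary Aim 1 estimate, and report the unweighted proportion as the sensitivity analysis. The participation weights in section 13.1 can multiply the design weights.
- Optionally, restate Table 9 by endpoint. A single overall design effect would mislead, because precision improves for undertreated diabetes and worsens slightly for other endpoints.

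The cost is SAP wording and a weighted analysis using data CCSS already holds; no new visits or measurements are needed. In the 8% illustration, underdiagnosis half-widths widen by 0.1 to 0.2 points and those for undertreated diabetes narrow.

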13.3 Aim 3 Analytic Plan

Hypotheses: 1) at baseline, underdiagnosis & undertreatment are associated with lower knowledge, self-efficacy, and medication adherence (if applicable), as well as a “self-controlling” health attitude among survivors; 2) at 1-year follow-up, compared with the control arm, the intervention arm will be associated with improved knowledge, self-efficacy, and adherence rates among survivors, and improved knowledge and self-efficacy among healthcare providers.

Baseline survivor-specific factors: Using data from all Aim 1 participants, determine whether those underdiagnosed and undertreated at the time of the 1st home visit have lower knowledge (i.e., less accurate recall of prior anthracycline or chest radiotherapy exposures [chi-square test]) and lower health-related self-efficacy [t-test or Wilcoxon rank-sum] compared with those not affected. Similarly, among those who report medications for the CV risk factors of interest, determine whether those undertreated have lower medication adherence (i.e., lower mean MMAS-4 scores [t-test or Wilcoxon

rank-sum]) vs. those not undertreated. Finally, determine if different health-related behavioral attitudes (“worried”, “collaborative” and “self-controlling”)⁶⁹ are associated with differential rates of underdiagnosis and undertreatment [chi-square test]. *A priori*, we hypothesize that the proportion undertreated will be greatest among “self-controlling” survivors vs. “collaborative” and “worried” (least undertreated) survivors. In subanalyses, we will analyze underdiagnosed participants (i.e., newly diagnosed per 1st home visit) separately from those undertreated (i.e., existing diagnosis but not meeting standard therapeutic goals) relative to the referent group (those without any abnormal CV risk factor). We also will use a combined logistic regression model to determine if knowledge, medication adherence, and health-related behavioral attitudes remain associated with underdiagnosis and undertreatment (combined and separately) after multivariate adjustment. Exploratory covariates are similar as before, and include sex, current age, insurance status, healthcare utilization, self-perceived CV risk, and family history of CV disease.

Post-intervention analysis: Among Aim 2 participants (and their designated healthcare provider), we will examine the differences between intervention and control groups following the 2nd home visit with respect to 1) survivor knowledge [chi-square test], 2) survivor self-efficacy [t-test or Wilcoxon rank-sum], 3) survivor-reported medication adherence [t-test or Wilcoxon rank-sum], and 4) provider-reported knowledge and self-efficacy [chi-square tests] related to the care of childhood cancer survivors. All analyses will be intent-to-treat and include all survivors and providers with available end points. Subanalyses can stratify these outcomes by initial underdiagnosis vs. undertreatment status. *We also will analyze practice changes over the 1-year intervention period using clinical records.* This includes comparing [chi-square test] whether documentation rates differ across study arms of: 1) any CV-related screening, 2) CV-related interventions [both lifestyle and drug prescriptions], and 3) treatment intensity (**Table 7** earlier). If any survivors share the same healthcare provider, we will apply bootstrap methods to account for the effects of clustering. In secondary analyses, we will determine, via logistic regression adjusting for randomization status, whether providers of survivors who remain undertreated have lower self-reported knowledge and self-efficacy related to the care of childhood cancer survivors vs. providers of survivors no longer undertreated.

Sample size: For covariates assessed at baseline in Aim 3, we will be able to detect differences $\geq 5\%$, RRs $\leq 0.8 / \geq 1.2$, and $\geq 20\%$ of 1 standard deviation (**Table 10**). Among randomized participants (240/arm) and subanalyses (e.g., analyzing undertreatment, underdiagnosis separately: $\sim 75-150$ /arm), detectable differences will be less.

Covariate frequency	Baseline* N=320:480	Post-intervention & subanalyses		
		240:240	150:150	75:75
10% (e.g., primary care provider self-efficacy towards childhood cancer survivorship care ^{27,28})	5%/17% RR 0.5/1.7	3%/20% RR 0.3/2.0	2%/22% RR 0.2/2.2	- /28% RR -/2.8
25% (e.g., MHLC self-controlling or worried typologies ⁶⁹ ; survivor anthracycline self-knowledge ⁷⁰)	17%/34% RR 0.7/1.4	15%/37% RR 0.6/1.5	12%/40% RR 0.5/1.6	8%/47% RR 0.3/1.9
60% (e.g., MHLC collaborating typology ⁶⁹ ; survivor radiotherapy self-knowledge ⁷⁰ ; high medication adherence ^{30,31,67,71,72})	50%/70% RR 0.8/1.2	47%/72% RR 0.8/1.2	44%/75% RR 0.7/1.3	37%/81% RR 0.6/1.3
% standard deviation (e.g., MMAS-4, ⁶⁰ survivor self-efficacy ⁵⁶)	20%	26%	33%	46%

Potential pitfalls / solutions: Self-reported medication adherence is not as accurate as data from pharmacy databases.¹⁰⁰ However, use of these databases is unlikely to be feasible even in large integrated health systems given the relative rarity of childhood cancer survivors. Given upfront randomization, any reporting biases should be similar across study arms. Should our study uncover a suggestive association with adherence, this would provide data to support the use of more expensive medication monitoring devices in a follow-up study.¹⁰⁰ We also anticipate some missing healthcare provider responses. It is possible that providers on the intervention arm who receive the SCP could be more motivated to respond (all providers will get clinically relevant results from home visits). We will closely monitor response rates for providers across the study arms, and will compare the characteristics of responding vs. non-responding providers using American Medical Association databases (physicians only) and publically available information from state licensing boards and the internet (physicians and other providers).^{28,102} In sensitivity analyses, we can examine the differences across study arms after adjustment for characteristics that appear to differ between responding and non-responding primary healthcare providers.

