8.1 Baseline Questionnaire

This will include items on: 1) past medical history, 2) current health and medication adherence, 3) lifestyle habits, and 4) attitudes towards healthcare and current mood (**Table 4; Appendix**).

TABLE 4. Components of baseline questionnaire, exclusive of questions on past medical history and lifestyle habits.

*Health-related self-efficacy⁵⁶	10-item (4-point Likert scale) survey (will be reduced to 5-items) that measures perceived ability to set-goals, cope and recover from setbacks. Results have been found to be a strong predictor of subsequent health behavior change. ⁹⁶
*PROMIS anxiety & depression^{57,58}	These domains (adult 4-item survey; all 5-point Likert scale) are of secondary interest. Prior research via a longer instrument (Profile of Mood States) did not show SCPs associated with mood changes or anxiety. ^{50,85}
*Multidimensional Health Locus of Control [MHLC]⁵⁹	18-item survey (6-point Likert scale) will classify participants with regards to their attitudes towards healthcare screening into “worried”, “collaborative” and “self-controlling” typologies, which have been associated with differential likelihoods of obtaining recommended screening in retrospective CCSS analyses. ⁷⁸
*Medication Adherence Scale (MMAS-4)⁶⁰	Well-established 4-item (0=high, 1-2=medium, 3-4=low adherence) instrument initially used to study hypertension, but since validated for other diseases. ¹⁰⁰ Will be administered separately for blood pressure, lipid, and diabetes medications. Secondary analyses will examine adherence by medication burden.

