13.2 Aim 2 Analytic Plan

Hypothesis: survivors randomized to the intervention will have a lower probability of having an undertreated CV risk factor compared with the control group at 1-year follow-up.

Primary analyses: We will describe baseline characteristics (including mean/median values of our target CV parameters) and proportions of underdiagnosis and undertreatment of our 3 CV risk factors. Our primary analysis will focus on the difference in the probability of having a CV risk factor undertreated after the 2nd home visit across the 2 study arms. As in Aim 1, undertreatment of hypertension, dyslipidemia, and diabetes at the 2nd home visit will be defined as blood pressure $\geq 130/80 \text{ mmHg}$, LDL ≥ 160 or triglyceride $\geq 150 \text{ mg/dL}$ (if fasting <10 hours: $\geq 200 \text{ mg/dL}$), or HbA1c $\geq 7\%$, respectively. Survivors with pre-diabetes at baseline will be undertreated at the 2nd home visit if fasting glucose $\geq 100 \text{ mg/dL}$ (non-fasting $\geq 140 \text{ mg/dL}$) or HbA1c $\geq 5.7\%$. As some survivors may contribute up to 3 outcomes (persistent hypertension, dyslipidemia, and diabetes/pre-diabetes), we will use generalized estimating equations (GEE), accounting for intra-individual correlation of the 3 outcomes, to estimate the overall intervention effect as a single parameter (3-element vector). If multiple survivors share the same primary healthcare provider (unlikely), we will apply random effects models in lieu of GEE given multiple

cluster types. Analyses will be conducted per intent-to-treat, and include all survivors with available end points.

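### Section 13.3 gives no unit of analysis for MMAS-4 adherence, which is scored per drug class; at baseline a condition-matched, survivor-clustered model would be more powerful than the named tests

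*Combined protocol and SAP*

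**What the plan says.** Table 4 in section 8.1 says of the MMAS-4: "Will be administered separately for blood pressure, lipid, and diabetes medications". The scale runs 0 to 4 ("0=high, 1-2=medium, 3-4=low adherence"). The same entry adds "Secondary analyses will examine adherence by medication burden", which is a further analysis and not a rule for combining the class scores.

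Section 3.3.1 sets a separate out-of-range threshold for blood pressure, lipids and HbA1c, so undertreatment is a label on a condition.

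Section 13.3 uses adherence in three places:
- at baseline, undertreated versus not ("among those who report medications for the CV risk factors of interest, determine whether those undertreated have lower medication adherence"), through "lower mean MMAS-4 scores [t-test or Wilcoxon" rank-sum;
- in a multivariable logistic model, as a single adherence term with no statement of which score enters;
- at 1 year, arm versus arm: "3) survivor-reported medication adherence [t-test or Wilcoxon rank-sum".

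The only clustering rule in 13.3 concerns providers: "If any survivors share the same healthcare provider, we will apply bootstrap methods to account for the effects of clustering". By contrast, 13.2 handles the same three-condition structure for Aim 2 with GEE, "accounting for intra-individual correlation of the 3 outcomes".

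**The concern.** A two-sample t-test or rank-sum needs one independent value per survivor. The instrument can yield one, two or three correlated values, and nothing in 13.3 says how they become one value or which undertreatment label each is compared with. At least three analyses fit the wording: all class scores pooled, one collapsed score per survivor, or one test per class. They differ in error rate, power and meaning, and the choice could be made after the data are seen.

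Adherence is named in both hypotheses of Aim 3. Section 13.3 says that a suggestive adherence association would support more expensive medication monitoring in a follow-up study. A spurious or a missed association would therefore have consequences.

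**Working it through.** **The plan's own figure.** Table 10 gives detectable MMAS-4 differences of 20, 26, 33 and 46% of 1 SD at 320:480, 240:240, 150:150 and 75:75. With (1.960 + 0.842) × sqrt(1/n1 + 1/n2), two-sided alpha 0.05 and 80% power, I get 20.2, 25.6, 32.4 and 45.8%. The row therefore reproduces with one independent score per person. It counts every survivor, although only medication users have a score, so it points to the intended unit rather than to the achievable power.

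**Assumptions.** The documents give neither the number of drug classes per user nor the between-class correlation (rho). I take three splits of users on 1/2/3 classes:
- A: about 68/28/4%, from independent use of the three classes at 40/30/20%
- B: 60/30/10%
- C: 40/40/20%

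Rho is 0.5 or 0.8.

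**If class scores were pooled with a survivor-level label** (arm is always one):
- Design effect = 1 + (Σm²/Σm − 1) × rho, where m is the number of classes.
- False-positive rate = 2 × (1 − Φ(1.96/√design effect)).
- Σm²/Σm is 1.420/0.900 = 1.578 for A (unrounded shares of all survivors), 2.7/1.5 = 1.800 for B and 3.8/1.8 = 2.111 for C.

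| Mix | Design effect, rho 0.5 | False-positive rate | Design effect, rho 0.8 | False-positive rate |
|---|---|---|---|---|
| A | 1.29 | 8.4% | 1.46 | 10.5% |
| B | 1.40 | 9.8% | 1.64 | 12.6% |
| C | 1.56 | 11.6% | 1.89 | 15.4% |

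Simulated t-tests on a 0-4 score (100 medicated survivors per arm) gave 7.8-10.0% at rho 0.5 and 10.4-14.0% at rho 0.8.

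**Pooling at baseline.** The result depends on the label. With mix B and 300 users, a survivor-level undertreated label gave 7.3, 9.8 and 13.3% at rho 0.3, 0.6 and 0.9. Condition-level labels varying independently within a survivor gave 4.6-5.4%, so no clear inflation. Labels that correlate within a survivor would bring some of it back.

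**Valid alternatives.** A per-survivor mean held 4.9-5.2%. One test per class is valid test by test; three at 5% have a family-wise rate of 1 − 0.95³ = 14.3% if independent.

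**Baseline power, collapsed score versus condition-matched clustered model** (assumed 250 medicated survivors):
- *Undertreatment follows adherence to the same class.* With 40% of treated conditions out of range, log-odds 0.35 per SD and rho 0.5, collapsed power was 75.1/72.8/74.8% for A/B/C, against 88.2/90.1/94.4% matched: gaps of 13.1, 17.3 and 19.6 points. A second set over rho 0.5-0.8 gave 65-72% against 78-90%, with gaps of about 10-24 points within a scenario.
- *Undertreatment follows overall adherence.* At rho 0.5 the pairs were 75.1 v 75.9, 73.7 v 75.9 and 73.1 v 77.7%: gaps of 0.8, 2.2 and 4.6 points. At rho 0.8 the gaps were 5-12. The second set, over rho 0.5-0.8, gave 64-72% against 67-81%, with gaps of about 1-10 points.

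In the second set the matched model held its false-positive rate at 4.2-6.6% and also beat three Bonferroni-corrected class tests.

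**One-year arm comparison.** A t-test on a per-survivor mean had a false-positive rate of 4.5-6.0% and power of 58-66%, against 56-67% for the clustered model. There is essentially no difference.

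**The case against.** A reader might infer that 13.3 commits the trial to an invalid test, or that adherence p-values will be too small. The documents do not support this. Nothing says the class scores will be pooled. The text compares survivors, and Table 10 reproduces with one score per person. One test per class also fits the way the scale is administered and keeps each drug with its own condition. The inflated rates describe an analysis that the wording permits but does not state.

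A second tempting reading is that collapsing to one score always costs power or defeats Aim 3. This does not hold either. At 1 year there is no condition to mismatch, and a per-survivor mean is fully adequate. At baseline the large loss appears when undertreatment is driven by adherence to the same class; with overall adherence as the driver it is small. If the effect is equal in all classes, a person mean has about 83% power against 79% for a single score (mix B, rho 0.6, 0.20 SD, 320:480). The Aim 3 hypothesis is itself worded at survivor level, so condition matching is a sharper question and not one the plan is bound to ask.

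It is also fair that the synopsis lists the Aim 3 arm comparisons as secondary endpoints, although section 3.1.3 calls Aim 3 primary. All of these objections stand. What remains is that the unit is unstated, and that a method the plan already uses for Aim 2 does better at baseline in both scenarios.

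**Conclusion.** The point holds as a gap in specification with a better method available, not as an error built into the plan. Section 13.3 does not state the unit of analysis for MMAS-4, how several scores combine, or which condition's undertreatment each score is set against.

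Pooling as independent would put the 1-year false-positive rate at roughly 8-15%. At baseline it would inflate with a survivor-level label, but not certainly with condition-level labels. A single score per survivor or a test per class is valid. At baseline a collapsed score gives up about 10-24 points of power under a same-class effect and about 1-10 points under an overall-adherence effect.

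Every size here rests on assumed class mixes, rho, number of medicated survivors and effect sizes; none is in the documents. The missing unit of analysis needs no assumption. The change is worth making, but it touches Aim 3 only. The Aim 2 primary analysis is unaffected.

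**What to change.** In 13.3, baseline adherence analysis: use one record per survivor per drug class. Relate each class's MMAS-4 score to undertreatment of the same condition (blood pressure drugs with blood pressure, lipid drugs with lipids, diabetes drugs with HbA1c). Fit a GEE with drug class as a covariate and robust standard errors clustered by survivor, following 13.2. State which score enters the multivariable logistic model.

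At 1 year, either use the same clustered model with one common arm effect, or keep the t-test/Wilcoxon on a per-survivor mean defined in advance. State that class scores will not be pooled as independent observations.

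While editing, reconcile the direction of the score: Table 4 gives 0 as high adherence, whereas 13.3 equates lower adherence with lower mean scores.

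The cost is SAP wording and a little more analysis, with no new data or participants. The small downside is that a model estimate replaces a simple two-group test.
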